#### 7.5.3 Prohibited Concomitant Therapy

Supportive care measures consistent with optimal subject care will be permitted throughout the study, as long as the therapy is not included in this section as prohibited.

Subjects are prohibited from receiving the following therapies during the Screening and Treatment Phase of this trial:

- Concurrent cancer therapy, including chemotherapy, radiation therapy, immunotherapy, or biologic therapy may NOT be administered to patients receiving study drug. If these treatments are administered the patient will be removed from protocol therapy.
- Investigational agents other than the study drug in this trial.
- Radiation therapy (allowed if  $\geq$  14 days prior to study registration).
- Cancer-Related Surgery (allowed if  $\geq$  14 days prior to study registration).
- Strong inhibitors and inducers of CYP2C8, CYP2D6, and P-glycoprotein (P-gp) should be used with caution.
- Medications that are sensitive or narrow therapeutic range substrates of CYP3A, CYP2C8, CYP2C9, CYP2C19, CYP2D6 should be avoided if possible. Other substrates of CYP2C8, 2C9, 2C19, 2D6, 3A, P-gp, OATP1B1, OATP1B3, OAT3, MATE1, and MATE2K should be used with caution.
- CYP3A4/5 inhibitors or inducers: Strong CYP3A4/5 inhibitors or inducers are prohibited from 14 days prior to the first dose of Tazemetostat to the end of the study (Appendix F). Note: Dexamethasone for CNS tumors or metastases, on a stable dose, is allowed.
- Live vaccines within 30 days prior to the first dose of trial treatment and while participating in the trial. Examples of live vaccines include, but are not limited to, the following: measles, mumps, rubella, chicken pox, yellow fever, rabies, BCG, and typhoid (oral) vaccine. Seasonal influenza vaccines for injection are generally killed virus vaccines and are allowed. However, intranasal influenza vaccines (e.g. Flu - Mist®) are live attenuated vaccines, and are not allowed. Patients may receive non-live versions of the COVID-19 vaccine.

## 7.6 Dose Modifications

The National Cancer Institute (NCI) Common Toxicity Criteria (CTCAE Version 5.0) for Adverse Events (CTCAE) will be used to grade toxicity (<http://evs.nci.nih.gov/ftp1/CTCAE/About.html>). See Table 3 for Dose Modification Tables for children and adults.

### 7.6.1 Non- Hematologic Toxicity

Non- Hematological dose limiting toxicity is defined as any Grade 3 or greater non-hematological toxicity attributable to the investigational drug with the specific exclusion of:

- Grade 3 nausea and vomiting of less < 3 days duration.
- Grade 3 liver enzyme elevation, including ALT/AST/GGT that returns to levels that meet initial eligibility criteria or baseline within 7 days.
- Grade 3 or 4 fever < 5 days duration.
- Grade 3 infection < 5 days duration.
- Grade 3 hypophosphatemia, hypokalemia, hypocalcemia or hypomagnesemia responsive to supplementation.
- Any Grade 2 non-hematological toxicity that persists for  $\geq 7$  days and is considered sufficiently medically significant or sufficiently intolerable by patients that it requires treatment interruption.
- **Note:** Allergic reactions that necessitate discontinuation of study drug will not be considered a dose-limiting toxicity.

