### 7.6.2 Dose Modifications for Non-Hematological Toxicity

If a patient experiences non-hematological dose-limiting toxicity as defined in Section 7.6.1, treatment will be held. When the toxicity resolves to meet eligibility parameters or baseline within 14 days of drug discontinuation, the patient may resume treatment at a reduced dose as below.

Patients who experience dose-limiting toxicity should have their dose reduced by 25% so that patients receive 75% of the original administered dose. For subjects taking 800 mg twice daily (dispensed as 4, 200-mg tablets twice daily), dosage should be reduced to 600 mg, dispensed as 3, 200mg tablets twice daily.

Doses reduced for toxicity will not be re-escalated, even if there is minimal or no toxicity with the reduced dose.

If toxicity does not resolve to meet eligibility or baseline parameters within 14 days of drug discontinuation, the patient must be removed from protocol therapy. If dose-limiting toxicity recurs in a patient who has resumed treatment, the patient must be removed from protocol therapy.

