#### 7.6.3 Hematologic Toxicity

Hematological dose limiting toxicity is defined as:

- Grade 4 thrombocytopenia or neutropenia, not due to malignant infiltration.
- Grade 3 thrombocytopenia that persists for  $\geq$  7 days.
- Grade 3 thrombocytopenia requiring a platelet transfusion on two separate days, within a 7-day period.
- Grade 3 thrombocytopenia with clinically significant bleeding.
- Neutropenia or thrombocytopenia that causes a delay of  $>$  14 days between treatment cycles (e.g. platelets  $<$  100K or ANC  $<$  1000).
- NOTE: Grade 3 or 4 febrile neutropenia will not be considered a dose-limiting toxicity.

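### A persistent Grade 2 toxicity that forces interruption is listed among the exclusions from a Grade 3-or-greater DLT definition, so the DLT recovery limit, recurrence rule and 24-hour report do not reach it

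*Combined protocol and SAP*

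**What the plan says.** Section 7.6.1 sets the threshold at Grade 3 or greater, "attributable to the investigational drug with the specific exclusion of" a bulleted list. The sixth bullet opens "Any Grade 2 non-hematological toxicity that persists for" 7 days or more. It is limited to events that are sufficiently medically significant or "sufficiently intolerable by patients that it requires treatment interruption". The last bullet is a Note: "Allergic reactions that necessitate discontinuation of study drug will not be considered a dose-limiting toxicity".

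The management rules depend on that definition. Section 7.6.2 begins: "If a patient experiences non-hematological dose-limiting toxicity as defined in Section 7.6.1, treatment will be held". If the toxicity has not resolved to eligibility or baseline parameters "within 14 days of drug discontinuation, the patient must be removed from protocol therapy". Section 7.6.2 also removes a subject whose DLT recurs after restart. Section 7.4 asks for a report within 24 hours of any suspected or confirmed DLT.

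Sections 7.2 and 7.6.2 give the 25% dose reduction to subjects with a DLT. Section 7.6 points to Table 3 without limiting it to DLTs. Section 7.6.5 applies Table 3 to the toxicities described in 7.6, and the table's title refers to adverse reactions generally.

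**The concern.** An exclusion list should remove events that would otherwise meet the definition. A Grade 2 event never meets a Grade 3-or-greater definition, so this entry does no work where it stands. Its content describes an event serious enough to stop the drug, which is what one would expect of a DLT criterion.

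What is at stake is what happens after the interruption. A subject with such an event has no stated limit on how long recovery may take, no clear restart dose and no rule for a second episode. If the event is not serious in the regulatory sense, it also has no 24-hour notice. Dosing is continuous for up to 26 cycles and subjects may be as young as 12, so the decision could plausibly arise. The documents give no frequency for it.

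**Working it through.** The plan states no figure to reproduce here. The check is a reading of the text, followed by short dose arithmetic.

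**Step 1: what the entry excludes.** Let A be all drug-attributable non-hematological events of Grade 3 or greater, and G the Grade 2 entry. A and G share no events, so A minus G equals A. The entry has no effect.

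**Step 2: how it compares with the other entries.** Leaving the Note aside, 7.6.1 lists six:

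| Entry | Qualifier | Direction |
|---|---|---|
| Grade 3 nausea and vomiting | under 3 days | mitigating |
| Grade 3 liver enzymes | recovery within 7 days | mitigating |
| Grade 3 or 4 fever | under 5 days | mitigating |
| "Grade 3 infection < 5 days duration" | under 5 days | mitigating |
| Grade 3 electrolyte falls | respond to supplementation | mitigating |
| Grade 2 toxicity | 7 days or more, significant or intolerable, requires interruption | aggravating |

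Five of the six excuse a brief or correctable event. Only the Grade 2 entry describes a worse one. Section 7.6.3 uses the same duration wording, "Grade 3 thrombocytopenia that persists for" 7 days or more, as a criterion that makes an event a DLT. Section 7.6.3 also closes its inclusion list with a note that febrile neutropenia is not a DLT. The allergic-reaction Note in 7.6.1 has the same form and would be redundant inside a list of exclusions. All three features fit a misplaced inclusion.

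**Step 3: which rules reach the event as written.**

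| Rule | Section | Trigger | Reaches the Grade 2 event? |
|---|---|---|---|
| Hold | 7.6.2 | DLT as defined in 7.6.1 | No, but the entry itself implies interruption |
| 14-day recovery limit | 7.6.2 | Toxicity that led to the DLT hold | No |
| Removal on recurrence | 7.6.2 | DLT | No |
| 24-hour report | 7.4 | Suspected or confirmed DLT | No |
| 25% reduction, text | 7.2, 7.6.2 | DLT | No |
| 25% reduction, Table 3 | 7.6, 7.6.5 | Toxicities described in 7.6 | Arguably yes |

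The 14-day sentence says toxicity rather than DLT, but it governs recovery after the DLT hold, so the narrower reading is the natural one.

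**Step 4: whether another section supplies what is missing.** Section 7.3 makes each new cycle depend on laboratory values and continued eligibility. Section 8.2 lets the investigator stop the drug for any adverse event. Section 11.3.3 records the action taken and has categories for both same-dose restart and dose decrease. Section 11.4.1 requires 24-hour reporting of serious events only. None gives this event a recovery limit, a restart dose or a recurrence rule.

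**Step 5: size of the dose ambiguity (Tables 2 and 3).**
- Adult, reduction for DLTs only, same-dose restart: 2 × 800 = 1600 mg/day.
- Adult, reduction reached through Table 3: 2 × 600 = 1200 mg/day.
- Difference: 400 mg/day, and 400/1600 = 25%. It is zero if every reader applies Table 3, so the range is 0 to 400 mg/day.
- Child: 520 × 0.75 = 390 mg/m² per dose, a difference of 0 to 130 mg/m² per dose. The 800 mg cap is reached at a BSA of 800/520 = 1.54 m². At the cap the reduced dose is 600 mg, so the largest difference is 200 mg per dose, ignoring rounding.

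**The case against.** The strongest objection is about the source. The text came from a PDF and its bullet levels are unreliable: part of criterion D in 4.2 is indented and the rest is not, and the Note in 7.6.1 appears as one more bullet. The Grade 2 line may have stood outside the exclusion list in the source. That possibility stands and limits confidence. Even so, no words in the entry make it a DLT, and the proposed rewording would be right in either case.

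Second, a reader might infer that the drug would simply continue. The documents do not support that, because the entry describes an event that requires interruption. A reader might also infer that the protocol calls for restart at full dose. It does not. Sections 7.6 and 7.6.5, with the general title of Table 3, favor the reduced dose, and nothing mandates 1600 mg/day. What stands is an ambiguity about the dose.

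Third, 7.4 covers suspected DLTs, so a site that sees the likely intent may report the event anyway. That would rest on the site's inference.

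Fourth, 7.3 refers to the Investigator Brochure and package insert, which are not in these documents. The gap is therefore shown for the protocol text only.

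Finally, leaving persistent Grade 2 toxicity to the investigator is a legitimate policy in a disease with few options. If that is the intent, however, the entry has no function where it stands.

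**Conclusion.** The point holds as a drafting fault in a safety rule. As written, the event is not a DLT, so the 14-day recovery limit, removal on recurrence and the 24-hour DLT report do not apply to it. The 25% reduction may or may not apply, which is worth 0 to 400 mg/day per affected adult and 0 to 130 mg/m² per dose per affected child. How many subjects this would touch is unknown, because the documents give no rate by grade, duration and need for interruption.

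A reader might go further and infer that the trial's safety conclusions or its two-stage design are compromised. They are not. The safety summaries in 12.6 and the interim rule in 12.7 make no use of DLT status, and neither does the sample size in 12.2. The effect is confined to individual dosing and safety reporting. The conclusion assumes that the extracted list order reflects the source and that the 14-day sentence belongs to the DLT hold. The point merits correction, with medium confidence.

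**What to change.** Take the Grade 2 entry out of the exclusion list in 7.6.1. State it as a second non-hematological DLT criterion: a drug-attributable Grade 2 toxicity lasting 7 days or more, medically significant or intolerable, and requiring interruption. Set the allergic-reaction Note apart from the list. Sections 7.6.2 and 7.4 then apply without further change.

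Judge recovery against baseline, as 7.6.2 already allows. The eligibility criteria in 4.2 set no threshold for most non-laboratory toxicities, and the nervous-system criterion accepts Grade 2 effects of prior therapy, so eligibility alone would be a poor recovery standard for a Grade 2 event.

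The edit is one moved line and one added sentence in an amendment. The clinical cost is that some subjects with persistent Grade 2 toxicity would have a mandatory dose reduction, or would leave treatment on recurrence. The sponsor should weigh that cost in confirming the intent.

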### 7.6.2 Dose Modifications for Non-Hematological Toxicity

If a patient experiences non-hematological dose-limiting toxicity as defined in Section 7.6.1, treatment will be held. When the toxicity resolves to meet eligibility parameters or baseline within 14 days of drug discontinuation, the patient may resume treatment at a reduced dose as below.

Patients who experience dose-limiting toxicity should have their dose reduced by 25% so that patients receive 75% of the original administered dose. For subjects taking 800 mg twice daily (dispensed as 4, 200-mg tablets twice daily), dosage should be reduced to 600 mg, dispensed as 3, 200mg tablets twice daily.

Doses reduced for toxicity will not be re-escalated, even if there is minimal or no toxicity with the reduced dose.

If toxicity does not resolve to meet eligibility or baseline parameters within 14 days of drug discontinuation, the patient must be removed from protocol therapy. If dose-limiting toxicity recurs in a patient who has resumed treatment, the patient must be removed from protocol therapy.

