## 6.1 Schedule of Events

Procedure:	Visit:	SCREENING (Windows outlined in Section 6.2)	CYCLE 1	CYCLES 2 AND BEYOND (WITHIN 72 HRS PRIOR)	END OF TREATMENT (WITHIN 14 DAYS OF LAST STUDY DRUG ADMINISTRATION)	FOLLOW UP (28 +/- 7 DAYS AFTER LAST DOSE OF TREATMENT)	SURVIVAL FOLLOW UP EVERY 90 +/- 14 DAYS AFTER LAST DOSE
Informed Consent		X					
Medical History, Demographic Information		X					
Clinical Exam		X	X	X	X		
Performance status (PS) 		X	X	X	X		
Vital Signs (VS) including height  , weight, and BSA 		X	X	X	X		
Numbered Pain Rating Scale 			X	X	X		
Labs (CBC diff, CMP) 		X	WEEKLY 	X			X 
Pregnancy Test (Urine or Serum) 		X	X	X			
INR		X					
Tibial x-ray 		X		X 			
Provide Study Drug for home administration			X	X			
Tumor disease evaluation 		X		EVERY 2 CYCLES 	X		
Tumor NGS 		X					
Circulating tumor DNA (ctDNA) 				X	X		
Provide and/or Review Subject Diary			X	X	X		
Concomitant Medication Review 		X	X	X	X		
Adverse Event Review 			X	X	X	X	
Survival Assessment							X

Abbreviations: VS=vital signs (blood pressure, temperature, pulse and respiratory rates, weight and height); CBC/diff=complete blood count and white blood cell differential; CMP = complete metabolic profile (sodium, potassium, chloride, bicarbonate, blood urea nitrogen, creatinine, glucose, alkaline phosphatase, AST, ALT, total bilirubin, protein), NGS Next Generation Sequencing

1 Performance status: Pediatric Karnofsky for subjects  $\geq$  16 years of age and Lansky for subjects 12-15 years of age; Adult ECOG score (18+)

UF-SC-001

2024-Aug-12

- 2 Numbered Pain Rating Scale , refer to Appendix G.
- 3 Laboratory tests at baseline need not be repeated if therapy starts within 72 hours of obtaining labs to assess eligibility. Labs are to be collected weekly for Cycle 1 (Days 1, 8, 15, and 22) +/- 72 hours. If patients have Grade 4 neutropenia then CBCs should be checked at least every other day until recovery to Grade 3 or until meeting the criteria for dose limiting toxicity. Automated differentials acceptable unless concern for blasts; then please obtain manual differential.
- 4 Female subjects of childbearing potential only.

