- 5 Patients must have either CT or MRI of primary and metastatic tumors, as well as whole body 18F-FDG PET/CT. Radiographic Tumor Assessment using RECIST 1.1 criteria. Imaging to be obtained every 2 cycles +/- 7 days from Cycle 1 Day 1 until disease progression or death. Screening imaging studies must be obtained within 30 days prior to start of protocol therapy.
- 6 Tumor NGS will be sent as part of standard of care, if not already done. If already done, results will be recorded as part of medical history review.
- 7 Circulating tumor DNA (ctDNA) results will be collected whenever obtained per standard of care.
- 8 Height and BSA only collected for pediatric subjects.
- 9 Adverse events, comed collection, and all sample collections, should be performed pre-dose at every cycle. The study drug will be provided at study visits, but self-administered at home throughout the trial. Cycles may be repeated for up to a total duration of therapy of 2 years (maximum 26 cycles), provided the patient meets the criteria for starting subsequent cycles and does not meet any of the criteria for removal from protocol therapy criteria.
- 10 Only to be completed for subjects <18 years of age. Screening tibial x-ray may have been performed within the past 6 months (180 days) before treatment (C1D1).
- 11 Tibial x-rays to be completed every 180 +/- 30 days only for those with open growth plates at screening.
- 12 CBC only – at each survival follow-up visit for five years, then yearly (at least once per calendar year) up to 10 years. Once a subject begins new anti-cancer therapy, they will be followed for survival only.

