### 7. STUDY TREATMENT

#### 7.1 Treatment Schedule/Administration

Tazemetostat will be administered orally twice daily with the dose beginning at the baseline visit (Cycle 1/Day 1) according to the Table 2 below.

Table 2: Tazemetostat Dosing

Baseline Criteria (age at enrollment)	Dose (continuous 28-day cycles)
Pediatric (12y - < 18y)	520 mg/m  /dose orally twice daily, not to exceed 800 mg orally twice daily, rounded up if between doses
Adult ( $\geq$ 18y)	800 mg orally twice daily (flat dose for adults)

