### 7.2 Overview of treatment plan

Tazemetostat will be administered at a dose of 520 mg/m^2/dose for pediatric patients 12- < 18 years of age (rounding up if between doses), and for adults  $\geq$  18 years of age, 800 mg, orally twice daily. The powder for suspension must be reconstituted prior to administration. Patients can take Tazemetostat without regard to meals, with no less than 8 hours between each dose. The oral suspension should be given by mouth immediately after the dose is prepared in the oral syringe. Patients should drink additional water after administration (about 4 ounces). For feeding tube dosing, administer directly into the feeding tube with the syringe. Rinsing with 10 mL of water for NG tubes and 40 mL of water for G-tubes is recommended. If vomiting occurs after taking oral suspension formulation, the dose should NOT be repeated and the next dose should be administered at the regularly scheduled time.

Therapy will be discontinued if there is evidence of progressive disease or drug related dose-limiting toxicity that requires removal from therapy (Section 7.6). A cycle of therapy is considered to be 28 days. Cycles may be repeated for up to a total duration of therapy of 2 years (maximum 26 cycles), provided the patient meets the criteria for starting subsequent cycles and does not meet any of the criteria for removal from protocol therapy criteria.

Pediatric drug dosages should be adjusted based on the BSA calculated from height and weight, measured within 7 days prior to the beginning of each cycle. Patients who experience dose-limiting toxicity should have their dose reduced by 25% so that patients receive 75% of the original administered dose.

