#### 7.6.4 Dose Modifications for Hematological Toxicity

If a patient experiences hematological dose-limiting toxicity as defined in Section 7.6.3, treatment will be held.

Counts should be checked every 3-4 days for thrombocytopenia and every other day for neutropenia during this time. If the toxicity resolves to meet eligibility parameters within 14 days of drug discontinuation, the patient may resume treatment at a reduced dose. The dose will be reduced by 25% so that patients receive 75% of the original administered dose. For subjects taking 800 mg twice daily (dispensed as 4, 200-mg tablets twice daily), dosage should be reduced to 600 mg, dispensed as 3, 200-mg tablets twice daily.

Doses reduced for toxicity will not be re-escalated, even if there is minimal or no toxicity with the reduced dose.

If toxicity does not resolve to meet eligibility parameters within 14 days of drug discontinuation, the patient must be removed from protocol therapy. If hematological dose-limiting toxicity recurs in a patient who has resumed treatment at the reduced dose, the patient must be removed from protocol therapy.

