### 8.3 Replacement of Subjects

Subjects may be replaced if they are not screen failures, have not completed at least 75% of intended doses in the first cycle, or are not discontinued for disease progression, toxicity, or any of the reasons listed in section 8.2.

Subjects who receive at least 75% of the intended doses in their first cycle will be evaluable for clinical response. Additionally, subjects who receive any dose will be evaluable for toxicity.

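### A Cycle 1 toxicity hold required by Section 7.6 can take a subject who resumes treatment out of the Section 8.3 evaluable count and make that subject replaceable, once more than 7 hold days fall inside the cycle

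*Combined protocol and SAP*

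**What the plan says.** **Hold and resume.** Section 7.6.2 (non-hematologic) and Section 7.6.4 (hematologic) both require treatment to be held after a dose-limiting toxicity. The first continues: "When the toxicity resolves to meet eligibility parameters or baseline within 14 days of drug discontinuation, the patient may resume treatment at a reduced dose". Its hematologic counterpart reads: "If the toxicity resolves to meet eligibility parameters within 14 days of drug discontinuation, the patient may resume treatment at a reduced dose". Neither has a separate rule for Cycle 1.

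**Evaluability.** Section 8.3: "Subjects who receive at least 75% of the intended doses in their first cycle will be evaluable for clinical response". It makes no exception for doses withheld under Section 7.6. It also does not define intended doses.

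**Replacement.** Section 8.3 begins: "Subjects may be replaced if they are not screen failures, have not completed at least 75% of intended doses in the first cycle". It then refers to subjects discontinued for progression, toxicity or a Section 8.2 reason. The sentence is awkwardly built. I read it as allowing replacement of a treated subject below 75% unless that subject was discontinued for one of those reasons.

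**Which set is counted.** The synopsis and Sections 3.1 and 4.1 set the goal as 29 evaluable subjects from up to 50 enrolled. Section 12.2 states the two-stage rule (stop at 2 or fewer responses in 9; reject the null at 10 or more in 29) for patients accrued. Section 12.7 places the interim after the first 9 subjects enrolled who have response data. Section 12.3 analyses ORR by intent-to-treat over all study patients.

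**The concern.** Section 7.6 tells the site to withhold drug, and Section 8.3 can then count the withheld doses against the subject. Take a subject who has a dose-limiting toxicity in Cycle 1, is held for 10 days as required, recovers, resumes and has the first on-treatment scan at about week 8. Everything was done according to protocol and a response assessment exists, yet the subject can fall out of the evaluable count and be replaced.

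The protection in Section 8.3 also runs in an odd direction. Its toxicity wording covers subjects who are discontinued. A subject whose toxicity ends treatment cannot be replaced; one who recovers and continues can be.

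Early toxicity is an outcome of treatment. An evaluable set that loses subjects because of it is partly selected for tolerating the drug. If held subjects respond less often than the others, ORR on that set is too high. If the 9- and 29-subject decisions were made on that set, the stated 5% type I error would no longer be assured.

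**Working it through.** **1. The plan's own figure.** Inputs from Section 12.2: null ORR 21%, alternative 45%, stop at 2 or fewer of 9, reject at 10 or more of 29. The exact rejection probability at response rate p is

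R(p) = Σ (x = 3 to 9) P[Bin(9, p) = x] × P[Bin(20, p) ≥ 10 − x].

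R(0.21) = 0.0485 and R(0.45) = 0.804. The stated 5% and 80% are reproduced.

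**2. The break point in days.** Section 7.2: "A cycle of therapy is considered to be 28 days". Section 7.1 gives twice-daily dosing from Cycle 1 Day 1. Intended doses = 28 × 2 = 56, and 75% of 56 = 42. With h hold days inside Cycle 1, doses received = 56 − 2h.

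| Hold days inside Cycle 1 | Doses | Share |
|---|---|---|
| 7 | 42 | 75.0% (still evaluable) |
| 8 | 40 | 71.4% |
| 10 | 36 | 64.3% |
| 14 | 28 | 50.0% |

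**3. When the hold must start.** Hold days inside Cycle 1 = min(hold length, 29 − first held day). For a 14-day hold:

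- first held day 15 or earlier: 14 days inside the cycle, 50.0% of doses
- Day 20: 9 days, 67.9%
- Day 21: 8 days, 71.4%
- Day 22: 7 days, 75.0%, however long the hold lasts

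Only a hold starting by Day 21 can breach the threshold. Section 6.1 sets the safety labs: "Labs are to be collected weekly for Cycle 1 (Days 1, 8, 15, and 22) +/- 72 hours". Findings at the Day 8 and Day 15 draws are exposed. A hold starting on Day 22 is not, although the 72-hour window lets that draw fall as early as Day 19.

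**4. Dependence on the undefined term.** If withheld doses are not intended doses, nothing is breached. If the rule counts milligrams, the limit tightens, because treatment resumes at a reduced dose. For 800 mg twice daily resumed at 600 mg twice daily, 75% of 28 × 1600 = 33,600 mg.

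- First held day 8: 7 × 1600 + (21 − h) × 1200 ≥ 33,600 gives h ≤ 2.3, so 2 full days.
- First held day 15: 14 × 1600 + (14 − h) × 1200 ≥ 33,600 gives h ≤ 4.7, so 4 full days.

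**5. Effect if decisions are made on evaluable subjects.** Let a fraction f of treated subjects drop out this way, and let them respond at k times the rate of the others. Hold the all-treated ORR at the null 21%. The evaluable ORR is then 0.21 / (1 − f + f·k).

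| f (assumed) | k (assumed) | Evaluable ORR | R(p) |
|---|---|---|---|
| 0 | – | 21.0% | 4.85% |
| 1% | 0 | 21.2% | 5.1% |
| 2% | 0 | 21.4% | 5.5% |
| 5% | 0 | 22.1% | 6.5% |
| 5% | 0.5 | 21.5% | 5.6% |
| any | 1 | 21.0% | 4.85% |

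The documents give neither f nor k.

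**The case against.** **The primary analysis is intent-to-treat.** Section 12.3 divides by all study patients. A held subject stays in that denominator, and any response stays in the numerator. A reader might infer that such a subject's response is discarded or that the primary ORR is biased; Section 12.3 does not support that. The objection stands and limits the point to replacement and to counts made on evaluable subjects. It does not remove the point. Accrual is still set by evaluable subjects, and Sections 12.2 and 12.7 do not say whether the 9 and the 29 are evaluable subjects or all treated subjects.

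**The sections do not strictly contradict each other.** One governs treatment, the other evaluability, and a site can follow both. Section 8.3 also does not say outright that a subject below 75% is not evaluable, and it says such a subject may, not must, be replaced. All of this is fair. Non-evaluability is the natural inverse reading, supported by the replacement sentence and the goal of 29, but it remains a reading.

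**The route is narrow.** A reader might take any hold longer than 7 days to breach the threshold; a hold starting on Day 22 or later does not. Under Section 7.6.3, Grade 3 thrombocytopenia without bleeding or repeated transfusion must persist for 7 days before it is dose-limiting. Section 7.6.1 excludes Grade 3 liver enzyme rises that recover within 7 days.

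**High hold rates look unlikely.** The same calculation at 10% or 15% affected, with no responses, gives 8.8% or 11.8%. The documents do not support relying on those cases. Section 1.4.1 reports 9% dose reductions for treatment-related events in a follicular lymphoma trial's interim update, not limited to Cycle 1. In the later follicular lymphoma report, thrombocytopenia and neutropenia of Grade 3 or worse were 3% each. These are other populations, so they bound nothing here, but they point toward the lower rows of the table in step 5.

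**Conclusion.** The point holds in limited form. Read with withheld doses counted as intended, Section 8.3 lets a subject with more than 7 hold days inside Cycle 1, from a hold starting by Day 21, leave the evaluable count and be replaced after following Section 7.6 and resuming. That is selection on tolerability, and it treats this subject less protectively than one discontinued for toxicity.

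The intent-to-treat ORR in Section 12.3 is not affected by the evaluability label itself. If the two-stage counts are made on evaluable subjects, type I error moves from 4.85% to about 5.1% to 6.5% for 1% to 5% of subjects affected and none responding. The 4.85% is unchanged if they respond at the same rate as the others. Both the rate and the non-response are assumptions. The size is modest, but the design has only 0.15 percentage points of room below 5%, and the ambiguity can be removed cheaply before it has to be settled with data in hand.

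**What to change.** Reconcile Section 8.3 with Sections 7.6 and 12.3 by adding to Section 8.3:

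- Doses withheld under Section 7.6.2 or 7.6.4 are not counted as missed intended doses.
- A treated subject with a Cycle 1 toxicity hold stays evaluable for response, counts as a non-responder unless a RECIST CR or PR is recorded, and is not replaced.

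No hold length, dose or treatment-stopping rule changes. The cost is a sentence or two of protocol text, and the ORR reported on evaluable subjects may be slightly lower.
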